Randomized Double---Blinded, Controlled
Trial to Compare the Effectiveness of
Sugammadex vs. Placebo to Prevent
Residual Neuromuscular Block in the Post---
Anesthesia Care Unit as Evaluated with a
Non---Invasive Respiratory Volume Monitor

NCT02728726

6/29/2017

f

Merck Investigator Studies Program (MISP) Protocol Template

Requirements for Submitting a Full Proposal

Section #1 - MISP Protocol Identification

Study Title:	Randomized Double-Blinded, Controlled Trial to Compare the Effectiveness of Sugammadex vs. Placebo to Prevent Residual Neuromuscular Block in the Post-Anesthesia Care Unit as Evaluated with a Non-Invasive Respiratory Volume Monitor
Request Date:	Protocol Version date 6/29/17
Institution Name:	Mayo Clinic, Jacksonville University of Texas - UT Health, Houston
Investigator Contact Information:	J. [name] Assistant Professor of Anesthesiology Department of Anesthesiology Mayo Clinic [name] O: [contact] E: [contact] [name] The University of Texas, UTHealth Department of Anesthesiology [name] [REDACTED] [REDACTED]

Section #2- Core Protocol

The Primary objective of this study is to determine whether patients who receive sugammadex immediately after tracheal extubation will exhibit a decrease in the incidence of postoperative residual paralysis and an associated decrease in the incidence of postoperative respiratory depression (which can precede critical respiratory events, CRE).

The Secondary objectives are to: a) determine whether patients receiving sugammadex will have a normal TOF ratio (>0.90) indicative of full neuromuscular recovery in the PACU; and b) to improve patient safety by documenting whether postoperative respiratory depression (decreased MV below 80% and 40% of predicted MV as assessed by a Respiratory Volume Monitor) is due to opioid administration vs. postoperative residual neuromuscular block (by comparing postoperative VAS scores and total opioid administered).

2.1 Objectives & Hypotheses

Hypotheses:

- A. After routine care and reversal of neuromuscular block as per usual clinical routine, and after tracheal extubation, surgical patients randomized to receive sugammadex vs. placebo in the OR will:
 - 1) have a lower incidence of "Decreased MV" [MV <80% MV predicted (MV_{PRED}) based on BSA] as well as lower average MV sustained at 15-30 minutes after PACU arrival than placebo patients
 - 2) have a lower incidence of "Low MV" as well as lower average MV at PACU discharge. An instance of "low MV" occurs when the measured MV is <40% MV predicted (MVPRED) based on BSA, for any contiguous 10 minutes in the 30 minutes leading up to PACU discharge.
- B. A smaller fraction of patients in the sugammadex group than in the placebo group spend more than 2 minutes in the PACU with a sustained "Low MV."
- C. A smaller fraction of patients in the sugammadex group than in the placebo group spend more than 2 minutes in the PACU with a sustained "Low MV" when corrected for PACU length-of-stay (LOS).
- D. The average %MV predicted is greater in the sugammadex group than in the placebo group.
- E. PACU LOS is shorter in patients receiving sugammadex as compared with placebo patients.
- F. Fewer patients in the sugammadex group have respiratory complications or require respiratory monitoring (O₂ desaturation, atelectasis, O₂ administration, CPAP, BiPAP, reversal medication).

	
 G. The sugammadex group has higher train-of-four (TOF) ratios than the placebo group at equivalent time points throughout their PACU stay. H. The ExSpiron is able to identify respiratory depression (defined as instances of MV <40% MV_{PRED} lasting at least 1 minute) occur prior to instances of SpO₂ <90% lasting at least 2 minutes). I. Lower MV measurements (corrected for total morphine equivalents administered) are correlated with lower TOF ratios.
--	--

2.2 Background & Rationale, Significance of Selected Topic & Preliminary Data	
Background and Rationale
 
A. Sugammadex Background.
 
Sugammadex is a relatively new compound, a gamma-cyclodextrin molecule that forms an 8-membered ring. Its internal ring diameter of approximately 7.4 Å is just sufficiently large to accommodate the external diameter of the aminosteroidal nondepolarizing neuromuscular blocking agents (NMBAs) rocuronium, vecuronium and pancuronium (in decreasing binding affinity).¹ The sugammadex-NMBA (rocuronium) complex has a very high affinity (association constant), such that once encapsulation of rocuronium by sugammadex occurs, dissociation is nearly non-existent. When administered to patients who received rocuronium-induced neuromuscular block, sugammadex binds free plasma rocuronium irreversibly, lowering the plasma concentration of free rocuronium. This promotes diffusion of free rocuronium from the neuromuscular junction back into the plasma, where the free rocuronium is again encapsulated. This removal of rocuronium from the neuromuscular junction reverses the neuromuscular block more rapidly and effectively than traditional anticholinesterases (neostigmine). Sugammadex is devoid of the side effects associated with neostigmine administration, and no anticholinergics (glycopyrrolate) need to be co-administered.² Sugammadex can reverse a rocuronium neuromuscular block of any depth, depending on the administered dose. Its time to complete reversal is also dose-dependent, but it averages 2-4 min, as opposed to reversal with neostigmine that requires 10-40 min for complete reversal. Sugammadex has been FDA approved for clinical use in the US. Sugammadex does not bind to most other anesthetic drugs or endogenous steroids, and has no affinity for any known receptors. It does bind to oral contraceptives and some rare antibiotics. There have been very few reported adverse events associated with sugammadex use, such as allergic reactions.³

--	--

B. Respiratory Volume Monitoring (RVM) Background:

An non-invasive RVM (ExSpiron, Respiratory Motion, Inc., Waltham MA) based on thoracic electrical impedance been shown to accurately monitor respiratory status in non-intubated patients, providing a real-time respiratory curve and measurements of minute ventilation (MV), tidal volume (TV) and respiratory rate.^{4,5,6,7,8} The ExSpiron system consists of two main components, a monitor and an electrode PadSet, which utilizes 3 adhesive electrode patches placed on the thorax, similar to ECG monitoring electrodes.

Simultaneous measurements of MV, TV, and RR with the RVM and a Wright monitoring spirometer demonstrated a precision error of 7.2% and 7.1% for MV and TV, and an accuracy error of 9.3% and 9.0%, respectively. Throughout the range of 4 breaths per minute (bpm) to 40 bpm and during erratic breathing, RVM measurements were highly correlated with measurements made with a Morgan diagnostic spirometer ($r = 0.96$, 95% CI: 0.93 to 0.99).⁹

In a recent study at the Massachusetts General Hospital in Boston published in the Journal of Trauma,¹⁰ the RVM evaluated 132 PACU patients following elective joint replacement surgery under general or regional anesthesia. This work demonstrated the effects of opioids on RVM measurements, and a stratification based on opioid sensitivity was proposed. This finding is relevant to the study proposed here, because the following categories were defined: "At-Risk" was defined as patients with a MV <80% of a given patient's predicted MV based on a body surface area formula. "Un-Safe" MV was considered to be <40% of Predicted MV sustained for at least 2 minutes.

[figure not shown]

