300 patients undergoing surgical procedures requiring general anesthesia with mechanical ventilation will be recruited and consent will be obtained. The subjects will be randomized preoperatively to receive in the OR following the procedure and prior to extubation either sugammadex (Group 1, n=150 patients) or placebo (Group 2, n=150 patients). In all patients, intraoperative surgical and anesthetic management will follow the usual clinical routine at the two enrolling institutions. Once surgery is finished, emergence from anesthesia will occur as per usual clinical routine until the clinician determines that the patient is ready for tracheal extubation. Once the decision to extubate the trachea is made, the patient will receive intravenously either sugammadex 2 mg/kg or placebo in a blinded manner. The patient's trachea will be then extubated, and postoperative anesthetic care will proceed as per usual routine. Patients will then be transferred to the PACU for postoperative care and recovery. (This methodology will ensure that all 300 patients will receive at least the current standard of clinical care. Of the 300 patients, 50% of them (n=150 patients) may benefit from the administration of sugammadex,

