2.7 Statistical Analysis and Sample Size Justification**A. Blinded Data Analysis:**

The investigator will be responsible for overall analysis of the data with assistance from Respiratory Motion staff in analysis of RVM data. The study will be double blinded with no knowledge of drug vs. placebo administration by investigator, clinical care providers or researchers performing the primary data analysis. A patient can be unblinded on an urgent basis if it is deemed necessary for the clinical care of the patient.

Study medication (sugammadex and placebo) will be prepared by the institutional pharmacy, and will be dispensed to the investigative team member according to the patient group assignment. The site study coordinator will call the pharmacy and alert them once a patient is enrolled in the study. The drug (sugammadex or placebo) will be prepared by the Pharmacy personnel according to the randomization sequence. The clinician administering the drug (sugammadex or placebo) will be blinded to the drug identity.

The investigators will be responsible for analyzing the study data, and the analysts will be blinded to patients' group assignment during the execution of the study. For the purpose of the final analysis, the official clinical database will not be unblinded until medical/scientific review has been completed and the investigators have been assured that the data are complete.

B. Statistical Analysis:

- a. Using Fisher exact test, we will compare across the two groups the incidence of:
 - i. Sustained MV<80%MV_{PRED} for at least 1 minute in the first 15-30 minutes after arrival in PACU
 - ii. Sustained MV<40% MV_{PRED} for more than 10 contiguous minutes of the last 30 minutes prior to PACU discharge
 - iii.. Sustained MV<40%MV_{PRED} for at least 2 minutes after opioid administration (amongst patients receiving opioids in the PACU)
 - iv. Sustained MV<40%MV_{PRED} for at least 2 minutes in the absence of opioids (amongst patients w/o opioids in the PACU)
 - v. Sustained MV<40%MV_{PRED} for at least 2 minutes after opioid administration (amongst patients receiving opioids in the PACU) when corrected for PACU LOS
 - vi. Sustained MV<40%MV_{PRED} for at least 2 minutes in the absence of opioids (amongst patients w/o opioids in the PACU when corrected for PACU LOS
 - vii. Adverse events, including:
 - 1. Respiratory complications (O₂ desaturation, atelectasis, respiratory status requiring advanced monitoring, etc.)

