 - 2. Respiratory interventions (O₂ administration, CPAP, BiPAP, medications, etc.)
 - 3. ICU or step-down unit transfer
 - viii. Normal TOF ratio (>0.90) at equivalent time points in the PACU (e.g. on arrival, at discharge, etc...)
- b. Using 2-sample t-tests we will compare:
 - i. Average MV during the 15-30 minutes after arrival at the PACU
 - ii. Average MV during the 30 minutes prior to the time cleared for PACU discharge
 - iii. Average LOS in the PACU
 - iv. Average pain scores
 - v. Average total opioid dose (morphine equivalents) in the PACU

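### Hypothesis C corrects low-MV incidence for PACU length of stay, itself a post-randomisation outcome, by an unstated method; using stay as a covariate or stratum can bias the arm comparison

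*Combined protocol and SAP*

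**What the plan says.** Section 2.1 states the low-MV comparison twice. Hypothesis B concerns the fraction of patients who "spend more than 2 minutes in the PACU with a sustained" low MV (below 40% of predicted). Hypothesis C is the same comparison "when corrected for PACU length-of-stay (LOS"). Hypothesis E, in the same list, is that "PACU LOS is shorter in patients receiving sugammadex as compared with placebo patients".

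On timing, the study procedures state: "The subjects will be randomized preoperatively to receive in the OR". Study drug is given once the decision to extubate is made, so the whole PACU stay follows both randomisation and dosing.

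In Section 2.7 B, the incidence items open with "Using Fisher exact test, we will compare across the two groups the incidence of". Item a.v is the low-MV incidence after opioids ("amongst patients receiving opioids in the PACU) when corrected for PACU LOS"). Item a.vi is its counterpart ("amongst patients w/o opioids in the PACU when corrected for PACU LOS"). Items a.iii and a.iv are the same two comparisons without the correction. Item b.iii then compares "Average LOS in the PACU" between arms by t-test.

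No section says whether the correction means a covariate, strata, a rate per hour, a share of the stay or a common window. The multi-factor ANOVA in item e does not supply it: there LOS is a dependent variable, examined against demographics.

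Under Section 2.7 C, C belongs to the remaining secondary hypotheses, tested only if A1 and A2 are both significant.

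**The concern.** The plan adjusts one efficacy outcome for another that it expects treatment to change. LOS may also depend on low MV: a patient who ventilates poorly may be kept longer, or a common factor such as frailty may drive both. Comparing patients of equal LOS across arms then compares unlike patients. If sugammadex shortens stay for other reasons, a sugammadex patient who stays as long as a placebo patient is more likely to have had low MV. The adjusted comparison shifts against the drug.

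A rate per hour carries a different risk. If low-MV episodes cluster soon after arrival, a shorter stay removes hours in which few events would have occurred, and the rate rises with no change in ventilation.

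Because Fisher's test takes neither a covariate nor a time denominator, the analyst will have to choose another method later. LOS as a covariate is the obvious choice and the one most open to bias. Hypothesis C could then miss a real reduction in low MV or suggest an excess that does not exist.

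**Working it through.** The plan gives no rate, power or sample size for Hypothesis C, and no LOS mean, SD or expected reduction, so there is no stated figure to reproduce. All inputs below are assumptions unless a source is given.

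**1. LOS as a covariate when low MV prolongs stay.** Let Y = 1 for low MV and A = 1 for sugammadex, with LOS normal, mean m + bY + cA and SD s. Here b is the minutes that low MV adds, and c is the drug's effect on LOS other than through low MV. By Bayes' rule the log odds of Y given A and LOS are the log odds given A plus

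[2b(LOS − m − cA) − b²] / (2s²).

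The coefficient of A therefore shifts by −bc/s².

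Inputs: low MV 22% vs 11%, borrowed from the A2 planning rates in Section 2.7 D. Those refer to PACU discharge, so using them for episodes at any time is an assumption. SD is 30 min.

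Unadjusted OR = (0.11/0.89)/(0.22/0.78) = 0.1236/0.2821 = 0.44.

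| b (min) | c (min) | −bc/s² | Adjusted OR, 22% vs 11% | Adjusted OR, no true effect |
|---|---|---|---|---|
| 15 | −10 | 150/900 = 0.17 | 0.438 × 1.18 = 0.52 | 1.18 |
| 20 | −15 | 300/900 = 0.33 | 0.438 × 1.40 = 0.61 | 1.40 |
| 30 | −15 | 450/900 = 0.50 | 0.438 × 1.65 = 0.72 | 1.65 |
| 30 | 0 | 0 | 0.44 | 1.00 |

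Simulated logistic analyses with 150 per arm agree with the formula. The chance of p<0.05 is about 73% unadjusted; adjusted, it is about 51%, 28% and 13% in the first three rows. With 22% in both arms, the adjusted false-positive rate in those rows is about 9%, 21% and 34%, nearly all towards harm from sugammadex.

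**2. Other meanings of the correction, with no drug effect on low MV.** Simulation with 2,000,000 patients per scenario, placebo median LOS 90 min and LOS ratio 0.8 on sugammadex. The low-MV hazard is either constant or concentrated early, and a cause shared by LOS and low MV is either present or absent. The correct ratio is 1.00.

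| Method | Constant hazard | Early hazard |
|---|---|---|
| LOS as covariate, shared cause (OR) | 1.41 | 1.39 |
| LOS as covariate, no shared cause (OR) | 0.99 | 0.99 |
| Events per time at risk (rate ratio) | 1.01–1.03 | 1.21–1.22 |
| Events per total LOS (rate ratio) | 1.04–1.07 | 1.23–1.24 |
| First 30 minutes from arrival (risk ratio) | 0.99–1.00 | about 1.00 |

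The mean share of stay spent in low MV, under a stationary process with a shared cause, was 0.095 in both arms. With a LOS ratio of 1.0, the covariate, rate and fixed-window analyses all gave about 1.00.

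**3. The uncorrected measure.** With constant hazard and a shared cause, whole-stay incidence was 23.4% vs 27.3% (sugammadex vs placebo) with no drug effect, solely because the sugammadex stay was shorter.

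**The case against.** The best defence is that C answers a real weakness in B. B counts any qualifying episode over the whole stay, so a shorter stay lowers it mechanically, as step 3 shows. Some allowance for unequal observation time is reasonable, and a disagreement between B and C could be informative. This stands, and the fix keeps that aim.

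A reader might infer that no form of the correction could be sound. The documents do not support that, since they fix no form. A fixed window is itself a way to handle unequal stay and shows no material bias here; a share of stay was unbiased in the scenario tried. A rate per hour redefines the endpoint rather than conditioning on LOS, and stays close to 1 under constant hazard.

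A reader might also infer that Hypothesis E, if true, is enough to produce bias. It is not. In the step 1 model, a drug that shortens stay only by preventing low MV has c = 0 and the adjusted OR is unchanged. A separate route is plausible, because Hypotheses D, F and G expect better ventilation overall, fewer interventions and higher TOF ratios, but the plan gives no size for it.

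Finally, the numbers do not describe a specified analysis. The plan names no logistic model, and a.v and a.vi are opioid subgroups with fewer than 150 per arm. The figures show direction and possible size only.

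**Conclusion.** The concern holds in a limited form. The correction in C, a.v and a.vi is undefined and cannot be carried out with the test named. Used as a covariate or stratum, LOS biases the arm comparison when two conditions hold: the drug affects LOS by a route other than low MV, and low MV prolongs stay or shares a cause with it. A rate per hour can also mislead if low MV clusters early. With the assumed inputs, an OR of 0.44 becomes 0.52 to 0.72; with no separate drug effect on LOS there is no shift.

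It would go too far to conclude that the trial's main result is at risk. A1, A2 and the sample size do not use the correction, and C is reached only after A1 and A2 succeed. The change is worth making because it is cheap and removes a choice that would otherwise be made late.

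**What to change.** In Section 2.1 and Section 2.7 B:

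- Redefine Hypothesis C as the incidence of MV below 40% of predicted, lasting at least 2 minutes, in one fixed window from PACU arrival, compared by Fisher's exact test in all randomised patients. The first 30 minutes is a natural choice, because A1 already needs data to that point. State how patients who leave earlier are counted; under the step 2 assumptions with a shared cause they were about 2% on sugammadex and 0.5% on placebo.
- State that LOS will not be used as a covariate or stratum in any arm comparison of low MV.
- Keep B (whole stay, uncorrected) and E (LOS) as separate outcomes, and read B knowing that it depends on length of stay.
- Drop the LOS-corrected items a.v and a.vi. Keep a.iii and a.iv, which serve secondary objective (b) on opioids versus residual block, but label them descriptive, because PACU opioid use is also determined after randomisation.

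The cost is wording only, since the respiratory volume monitor already records throughout the PACU stay. The downside is that low-MV episodes after the window count in B but not in C.

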general anesthesia and planned extubation in the OR. After a thorough review of the study. Sufficient time will be given to the patients, parents, guardians or legal representative to ask questions and decide on participation.

- d. Location where study will be performed: University

	
of Texas, UTHealth at Houston and Mayo Clinic, Jacksonville, Florida operating holding areas, operating and recovery rooms, and intensive care units as applicable.
 
e. Personnel who will conduct the study include PI and research team members.
 
10) Subject fees: There are no fees for this study.
 
11) Procedures to protect subject confidentiality: A unique study ID number will be assigned to each subject as a means to de-identify the study data. A code will be kept separately with the PI. Study files will be kept in a locked office in a locked cabinet or a password-protected computer with encrypted study files. The location will be the PI office with restricted access. The code will be locked separately from study files in the PI office.
 
a. Certificate of Confidentiality: N/Ab. How data will be coded, recorded, and stored to protect confidentiality: All data will be de-identified. All data will be linked to the subject study ID by a code.c. Data will be analyzed by institutional biostatisticians at UTHealth at Houston.d. Parties who will have access to the data, including the key to the identity code: only [name] and J. [name] and primary study staff will have access to the master study log/key. Other investigators and the clinical and engineering staff at Respiratory Motion, Inc. will only have access to de-identified data.e. Parties who will have access to research records: Investigators on the study, Respiratory Motion, Inc. will have access only to de-identified records.f. Collaboration: This study is performed in collaboration with Respiratory Motion, Inc.g. Alternatives: The alternative to participating in this study is not participating.h. How new information will be conveyed to the study subject and how it will be documented: Other than the initial explanation of the purpose and plan for the study, we don't expect new information to
--	---

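### Hypothesis H is biased toward the MV monitor warning first and cannot be interpreted as written: unequal durations, no look-back limit, no count of dips without a desaturation, and no specified analysis

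*Combined protocol and SAP*

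**What the plan says.** Section 2.1, hypothesis H, expects ExSpiron instances of MV <40% of predicted "lasting at least 1 minute) occur prior to instances of SpO₂ <90% lasting at least 2 minutes". That is the whole rule.

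Other MV <40% criteria that state a duration are stricter:

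- Section 2.2 B, on the earlier PACU cohort: for the Un-Safe category, "MV was considered to be <40% of Predicted MV sustained for at least 2 minutes".
- Section 2.1, hypotheses B and C: more than 2 minutes.
- Section 2.7 B, items a.iii to a.vi: 2 minutes, for example "for at least 2 minutes in the absence of opioids". Item e uses the same 2-minute outcome.
- Hypothesis A2 and item a.ii: 10 contiguous minutes.

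The only other 1-minute rule, item a.i, concerns a different threshold (MV <80%).

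Section 2.7 B contains no analysis of H. Its sensitivity and specificity item (d) is about the effect of sugammadex, and its correlations (f) relate MV to TOF ratio, opioid dose and pain score, not to SpO2.

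On recording, section 2.5 A has the ExSpiron running from before extubation, through transport, into the PACU (item 1). Physiologic monitoring is described only for the PACU, under the standard protocol and with no sampling interval (item 6).

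On who analyses, section 2.5 B item 11c says "Data will be analyzed by institutional biostatisticians at UTHealth at Houston". Section 2.7 A makes the investigator responsible for the overall analysis, "with assistance from Respiratory Motion staff in analysis of RVM data".

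**The concern.** H compares two signals in the same patient, and its rule favours one of them in three ways.

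1. The device under evaluation has to persist for 1 minute and the comparator for 2. The shorter MV <40% duration appears only here, and no reason is given.
2. Any earlier dip satisfies the ordering. A dip at extubation or in transport, where no SpO2 recording is described, could be credited as a warning of a desaturation late in the PACU stay.
3. Dips followed by no desaturation cost the device nothing, so a monitor that dips often cannot be told apart from one that predicts.

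H has no treatment arms, so blinding to allocation does not guard against these choices. At stake is a claim about the monitor's early-warning value, not the sugammadex comparison.

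**Working it through.** The plan gives no expected proportion, power or sample size for H, so there is no figure to reproduce. From the plan: 1 minute for MV, 2 minutes for SpO2, an ordering requirement and no window. Assumed, because the documents give no values: rates and lengths of episodes, and the time of desaturation.

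**Unequal durations.** Take two identical, independent episode processes over 120 minutes, with episodes at 0.5 or 2 per hour and exponential lengths averaging 1, 2 or 5 minutes. Simulate which qualifying event comes first (40,000 runs per setting).

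| Rule (MV / SpO2) | MV first, patients with both events | MV first, all patients with a desaturation |
|---|---|---|
| 1 min / 2 min, by time of qualifying | 52-58% | 16-53% |
| 1 min / 2 min, by onset | 51-57% | 16-52% |
| 2 min / 2 min | 50-51% | 6-46% |

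The last column is lower because some desaturations have no MV event at all. H does not say which denominator applies. Within a given setting, moving from 2/2 to 1/2 by time of qualifying raises the last column by between 6 points (29.5% against 23.9%) and 24 points (44.9% against 21.3%).

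The 52-58% also depends on the assumed rates. If episodes were so frequent that both events always occurred, the onset comparison would approach 1/(1 + exp(−1/m)) for mean length m: 73%, 62% and 55% for m = 1, 2 and 5 minutes.

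If both signals start together and both last at least 2 minutes, MV leads by 2 − 1 = 1 minute when qualifying times are compared. They tie when onsets are compared. H does not say which is meant.

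**No look-back limit.** Let qualifying dips arise at rate r per hour, unrelated to desaturation. The chance that at least one precedes a desaturation at time T minutes is 1 − exp(−rT/60). With a look-back of W minutes it is 1 − exp(−rW/60). For T = 60 and W = 15:

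| r per hour | No window | 15-minute look-back |
|---|---|---|
| 0.1 | 1 − exp(−0.1) = 10% | 1 − exp(−0.025) = 2.5% |
| 1 | 1 − exp(−1) = 63% | 1 − exp(−0.25) = 22% |
| 2 | 1 − exp(−2) = 86% | 1 − exp(−0.5) = 39% |

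Over a wider range, the figure without a window runs from 5% (0.1 per hour, T = 30) to nearly 100% (4 per hour, T = 120).

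**The case against.** A reader might infer that a finding of MV first is guaranteed by the definitions, or that the trial would report it even if the two signals were unrelated. The documents do not support that. A desaturation with no earlier dip counts against H, and the chance of a coincidental earlier dip depends on a rate that is nowhere stated. The nearest figure, about 22% of patients leaving the PACU with MV <40% (section 2.7 D), would cap chance precedence at about 22% if only those patients ever dipped. It describes discharge, however, and may understate 1-minute dips over the whole stay, so it does not settle the matter.

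It can also be said that different durations suit different purposes. The 2- and 10-minute rules define outcomes compared between arms, while H is about early detection, and the plan has no single MV duration. That is fair, and a shorter MV duration is not an error in itself. It does need a reason, and a comparison that does not reward the device for the shorter wait.

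The device maker's part should not be overstated. It gives assistance and sees only de-identified data, and analysis is already assigned to the UTHealth biostatisticians. Care staff do not see numerical MV or trends, so MV readings should not prompt treatment that changes later SpO2. What remains is that the plan does not say who runs the comparison in H.

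Finally, H is not among the objectives stated in section 2, is unpowered, and is tested only if A1 and A2 both succeed (section 2.7 C). That limits the impact, but does not make the rule interpretable.

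**Conclusion.** The point stands in this form: H is biased toward MV first, and its result cannot be interpreted without a common time basis, a look-back limit and a count of dips with no later desaturation. No analysis in section 2.7 supplies these.

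The unequal durations have a modest effect among patients with both events (about 52-58% against 50%), under the assumed episode rates and lengths. The missing window is potentially the larger problem, but its size is unknown: 10% to 86% chance precedence at 60 minutes for assumed unrelated dips at 0.1 to 2 per hour. The direction of the bias follows from the text; its size rests on those assumptions.

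The change should be made before the data are analysed. The primary and key secondary results are unaffected.

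**What to change.** Add an analysis of H to section 2.7 that states:

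- the same minimum duration for both signals, with onset compared with onset. Two minutes matches most of the plan's MV <40% criteria; the 1-minute rule can stay as a labelled sensitivity analysis;
- restriction to the period when both MV and SpO2 are recorded;
- an MV instance counts as a warning only if its onset falls within a look-back before the SpO2 onset, fixed before the data are analysed. Fifteen minutes is an example, not a figure from the documents;
- two shares reported together: desaturations with no MV warning, and MV instances with no later desaturation;
- that the UTHealth biostatisticians named in section 2.5 B item 11c run this comparison.

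The cost is wording, with no new staff. H already needs SpO2 timed finely enough to establish a 2-minute episode, and the fix needs that same record. Because no sampling interval is given, the team should confirm that the standard-care record is fine enough; if it is not, neither H nor the amended version can be evaluated. The real downside is a less favourable lead figure for the device.
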